The Effectiveness of the Video Conferencing Telerehabilitation Method, Delivered in One on One and Group Sessions, in Urinary Incontinence Cases.

Study Protocol and Statistical Analysis Plan (SAP) (Pages 1 – 21)

November 15,2021

**The Effectiveness of the Video Conferencing
Telerehabilitation Method, Delivered in One on One and Group Sessions, in Urinary
Incontinence Cases.**

Study Protocol (Pages 2-6)

November 15,2021

Study Protocol

Study titled “The Effectiveness of the Video Conferencing Telerehabilitation Method, Delivered in One on One and Group Sessions, in Urinary Incontinence Cases.” was approved by Marmara University Faculty of Medicine Ethical Committee at the meeting on 30.11.2020 with approval number: 1195 (Annex-1).

The legal representatives of the patients who participated in the study will be informed about the aim, duration and the programs to be applied throughout the study. Volunteer Information Form will be signed and approved in accordance with the standards deemed appropriate by the Ethical Committee of Marmara University Faculty of Medicine. The study will be conducted in accordance with the Declaration of Helsinki.

Hypothesis of the Study

H0: With one on one video conference method, exercise training is no superiority of exercise training with group video conferencing method in urinary incontinence.

H1: Exercise training with one on one video conference method is more effective in increasing muscle strength in patients with urinary incontinence.

H2: One on one videoconferencing and exercise training are more effective in reducing the degree of incontinence in patients with urinary incontinence.

H3: Exercise training with one on one videoconferencing method is more effective in increasing the quality of life in patients with urinary incontinence.

H4: Exercise training with one on one videoconferencing method is more effective in increasing patient satisfaction in patients with urinary incontinence.

H5: Exercise training with one on one video conference method is more effective in increasing sexual function in patients with urinary incontinence.

H6: Exercise training with one on one videoconferencing method is more effective in increasing exercise adherence in patients with urinary incontinence.

Randomization of the Study Groups

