Individuals with Urinary İncontinence applying to Göztepe [name]. Süleyman Yalçın Şehir Hastanesi will be invited to participate in the study. Individuals who volunteered to participate and whom met the criteria for participation will be randomized with simple random sampling method and will be

divided into two groups. In both groups participants will receive same exercise program and physiotherapist will follow up the exercise program every week by video conference method. While only the physiotherapist and the patient will take part in the one-on-one group, there will be a physiotherapist and 8 patients in the group sessions.

Inclusion Criteria

18-65 aged

BMI 18-30 kg/m²

Being diagnosed with stress incontinence or mixed incontinence (dominantly SUI)

Mild or moderate incontinence (mild SUI; urinary incontinence with coughing, sneezing, laughing, or any strenuous activity. Moderate; urinary incontinence with carrying, pushing, lifting, walking, and any light physical activity)

Exclusion Criteria

Pregnancy

Ongoing vulvovaginitis or urinary tract infection or malignancy

Pelvic floor muscle strength is between 0-1 according to the Modified Oxford Scale,

Previous surgery for SUI

Problems with vision or inability to understand given commands

Conservative therapy in the last 6 months

Allergic reaction to the gel used with the perinometer/probe

Evaluations

Evaluation parameters will be applied at the baseline, at the end of 4-weeks treatment program, at the end of 8 weeks treatment program. Outcome measures and applied evaluations are shown in Table 1.

Table 1. Outcome measures and evaluation methods

Primary Outcome Measures	Evaluation Methods
Muscle Strength	-PERFECT Scheme -Surface Electromyography

Secondary Outcome Measures	Evaluation Methods
Symptom Evaluation	-1 hour pad test -The International Consultation on Incontinence Questionnaire-Short Form - Urogenital Distress Inventory- 6 (UDI-6) - Incontinence Impact Questionnaire-7 (IIQ-7) - Overactive Bladder -Validated 8- Question Awareness Tool (OAB-V8)
Patient Satisfaction	Visual Analog Scale (VAS)
Exercise Adherence	VAS Broome Pelvic Floor Muscle Exercise Self- Efficacy Scale
Sexual Function	Female Sexual Function Scale (FSFI)

Treatment Program

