The exercises which given the both groups compose same exercise protocols for 8 week. The exercise protocol includes pelvic floor muscle training, diaphragmatic breathing exercise and core exercise will be given the all participants. The participants in the study will be followed up with video conferencing method by weekly.

Group I (one on one video conferencing group): In this group, exercise follow-up and transition to the next exercise phase will be realized with one-on-one video conference interviews.

Group II (group sessions video conferencing group): In this group, exercise follow-up and transition to the next exercise stage will be realized with group video conference sessions consisting of 8 participants.

The Effectiveness of the Video Conferencing Telerehabilitation Method, Delivered in One on One and Group Sessions, in Urinary Incontinence Cases.

Statistical Analysis Plan (SAP) (Pages 7 –8)

November 15,2021

Statistical Analysis Plan (SAP)

In the analysis of the data to be obtained in the study, the significance will be evaluated at the $p < 0.05$ level with the SPSS 22.0 statistical program at the 90% confidence interval. In the evaluation of variables; If the number of cases is sufficient, its conformity to the normal distribution will be questioned with the Kolmogorov Smirnov test and normal distribution graphs. In the examination of the variables, appropriate statistical tests will be applied depending on the provision of parametric or non-parametric test conditions. Normally distributed variables will be expressed as mean and standard deviation, and non-normally distributed variables will be expressed as numbers and percentages. If the groups fit the normal distribution, the evaluation results at the beginning, 4th week and 8th week will be compared with ANOVA, if the normal distribution is not met, comparisons will be made with Kruskal Wallis and appropriate post-hoc tests. In the correlation analysis, the appropriate Spearman or Pearson correlation analysis methods will be preferred. Chi-square test will be used in the evaluation of binary data.

The Effectiveness of the Video Conferencing Telerehabilitation Method, Delivered in One on One and Group Sessions, in Urinary Incontinence Cases.

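### Group II is followed up in sessions of 8, but the SAP's named tests take no account of session groups; a between-arm comparison needs to be written out and a clustering-aware sensitivity analysis set beside it

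*Combined protocol and SAP*

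**What the plan says.** The protocol's null hypothesis, under Hypothesis of the Study, contrasts the two modes of delivery: "With one on one video conference method, exercise training is no superiority of exercise training with group video conferencing method". H1 to H6 each claim that one-on-one delivery is better on one outcome; H1, on the primary outcome, reads "Exercise training with one on one video conference method is more effective in increasing muscle strength in patients with urinary incontinence".

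Under Randomization of the Study Groups, individuals are randomised to two arms, and "In both groups participants will receive same exercise program and physiotherapist will follow up the exercise program every week by video conference method". For the group arm, "there will be a physiotherapist and 8 patients in the group sessions". Treatment Program says the same at more length. In Group I, "exercise follow-up and transition to the next exercise phase will be realized with one-on-one video conference interviews"; in Group II, "exercise follow-up and transition to the next exercise stage will be realized with group video conference sessions consisting of 8 participants".

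On timing, "Evaluation parameters will be applied at the baseline, at the end of 4-weeks treatment program, at the end of 8 weeks treatment program". The SAP compares the results at these three times by ANOVA, or by Kruskal-Wallis with post-hoc tests if normality fails, and uses chi-square for binary data, with significance at p < 0.05. Its general rule for choosing a test is that "appropriate statistical tests will be applied depending on the provision of parametric or non-parametric test conditions". It names no session-group term, mixed model or ICC.

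**The concern.** Only one arm is nested. Eight Group II participants share a weekly session, and their move to the next stage of exercise is handled there. Their outcomes may therefore resemble each other more than those of eight participants seen singly. The named tests assume independence, and the SAP's rule for choosing among them looks only at distribution.

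If the correlation within session groups is positive, the estimated arm difference is not biased by it, but its standard error is too small. A difference between delivery modes, which is the question the trial asks, would then be declared too often when there is none.

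**Working it through.** **Inputs from the documents.** Session size 8 in Group II; cluster size 1 in Group I; significance level 0.05; individual allocation to two arms. There is no stated power or ICC figure to reproduce.

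**Assumptions.** Equal arms, equal total variance, two-sided testing (sidedness is not stated), session groups with fixed membership, 1 to 6 groups (8 to 48 per arm), ICC 0.01 to 0.20.

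**Formulae.**

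- Design effect in Group II: 1 + (8 − 1) × ICC = 1 + 7 × ICC.
- Variance of the arm difference relative to the independence value: (1 + 1 + 7 × ICC)/2 = 1 + 3.5 × ICC. The SE ratio s is its square root.
- True size of a nominal 5% test: 2 × [1 − Φ(1.96/s)].
- Planned-test p that corresponds to a true 0.05, with the ICC taken as known: 2 × [1 − Φ(1.96 × s)].

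| ICC | 1 + 3.5 × ICC | s | True size | Simulated size | p needed |
|---|---|---|---|---|---|
| 0.01 | 1.035 | 1.02 | 5.4% | 5.4-5.5% | 0.046 |
| 0.05 | 1.175 | 1.08 | 7.1% | 6.9-7.2% | 0.034 |
| 0.10 | 1.350 | 1.16 | 9.2% | 9.1-9.4% | 0.023 |
| 0.20 | 1.700 | 1.30 | 13.3% | 13.5-14.2% | 0.011 |

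The simulated column is a two-arm ANOVA with 40,000 replicates per setting. At ICC 0 the test holds about 5%. Kruskal-Wallis on two arms behaves alike: 6.6-7.1%, 8.8-9.2% and 12.5-13.7% at ICC 0.05, 0.10 and 0.20.

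**Unequal arms.** Simple randomisation can give unequal arms. With 40% or 60% of participants in Group II, the last cut-off at ICC 0.20 becomes 0.008 or 0.014.

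**Session variance estimated rather than known.** With K session groups and n = 8K per arm, put v1 = 1/n and v2 = (1 + 7 × ICC)/n. The Satterthwaite degrees of freedom are (v1 + v2)² / [v1²/(n − 1) + v2²/(K − 1)]. For K = 4 and ICC 0.05 this gives 8.6, a critical value of 2.28, and a required planned-test p of about 0.016 instead of 0.034. For 3 and 6 groups it is about 0.010 and 0.023. These figures take the estimated variances at their assumed values.

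**Analysis of change.** If the session effect arises only after baseline, the ICC of the change score is the week-8 ICC divided by (2 − 2r), where r is the correlation between time points. At a week-8 ICC of 0.05 and r of 0.3, 0.5 and 0.7:

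- 0.05/1.4 = 0.036
- 0.05/1.0 = 0.050
- 0.05/0.6 = 0.083

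The formulae above then give sizes of about 6.5%, 7.1% and 8.5%. The satisfaction items (Annex 7) and the adherence scale (Annex 8) ask about treatment already given. They have no pre-treatment value, so the single-time-point table applies to them.

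**The case against.** Four objections have force.

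- **No document figure supports a positive ICC.** Content is standardised across arms, and muscle strength, the primary outcome, may show little or no clustering. This stands, so the size of the problem is conditional throughout.
- **The criticised test is not written out.** The ANOVA and Kruskal-Wallis sentence names time points, not arms. This also stands: the missing arm comparison comes first, and clustering matters for whatever comparison is then specified.
- **The physiotherapist is named in the singular.** If one person serves everyone, therapist differences cannot cause session-group correlation. Shared sessions and shared progression still can. If there are several physiotherapists, Group I may be clustered too.
- **Membership may rotate.** The text available does not say that groups are fixed. If they change from week to week, the nesting is weaker and the formulae are only approximate.

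A reader might infer that every arm difference with p between 0.01 and 0.05 is unsafe. With the ICC taken as known, that needs an ICC of about 0.21, since (2.576/1.960)² = 1.727 and (1.727 − 1)/3.5 = 0.208. At ICC 0.05 the exposed band is only 0.034 to 0.05.

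A reader might also infer that the clustered analysis should decide every outcome. The documents do not support that either. With 2 groups and no true clustering, power for an assumed 0.8 SD effect falls from 59% to about 52% if the variance is inflated for ICC 0.05, and to about 35% if it is inflated for 0.20.

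**Conclusion.** The point holds in conditional form. Only Group II is nested, and none of the SAP's named tests allows for it. Under the stated assumptions the true two-sided size is about 5.4%, 7%, 9% and 13-14% at ICC 0.01, 0.05, 0.10 and 0.20. With the ICC known, planned-test results with p above about 0.046, 0.034, 0.023 or 0.011 respectively would not stay below 0.05. With session variance estimated from few groups, the cut-off is lower.

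Whether any of this occurs depends on an ICC that the documents do not give. It is least likely to matter for muscle strength and most plausible for satisfaction (H4) and adherence (H6). The absence of a sample size from the text available is not counted against the plan. This is a cheap improvement, not a defect that invalidates the trial.

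**What to change.** 1. Write out the between-arm comparison for each H1 to H6 outcome, including sidedness.
2. Record each Group II participant's session group, weekly if membership changes, and the physiotherapist if there is more than one.
3. Keep the planned test as the main result, and fix in advance a sensitivity analysis to report beside it:
   - **Four or more fixed session groups:** a partially nested mixed model with a random session-group effect in Group II only, arm-specific residual variance and Satterthwaite degrees of freedom. Four is not a sharp threshold. At ICC 0.05 the session variance is estimated as zero in about 44% of simulated trials with 4 groups and 38% with 6, so a zero estimate is not evidence of no clustering.
   - **One to three groups:** multiply the Group II variance by 1 + 7 × ICC over 0 to 0.20, and report the largest ICC at which the difference stays below 0.05, with no pass/fail rule.
   - **Rotating membership:** state that neither method applies exactly and report the inflation range as approximate.
4. Where the planned test is significant and the sensitivity analysis is not, word the conclusion as sensitive to session-group clustering.

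The cost is one or two recorded variables and some SAP wording, with no extra patients or procedures. The downside is wider intervals in the sensitivity analysis and more cautious wording for some results. With 4 groups, an assumed 0.8 SD effect and ICC 0, power is about 88% for the planned test and about 80% for the mixed model.

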Annex 3. Assessment of Muscle Strength

PERFECT SCHEME					
	Power (P)	Endurance (E)	Repetitions (R)	Fast Contraction (F)	Every Contraction Time (ECT)
1					
2					
3					
MEAN					

Surface EMG			
	Resting tone	Maximum Voluntary Contraction (MVC)	Pelvic Floor Muscle Endurance
1			
2			
3			
Mean			

Annex 4. International Consultation on Incontinence Questionnaire-Urinary Incontinence Short Form

Initial number

ICIQ-UI Short Form

CONFIDENTIAL

DAY MONTH YEAR

Today's date

Many people leak urine some of the time. We are trying to find out how many people leak urine, and how much this bothers them. We would be grateful if you could answer the following questions, thinking about how you have been, on average, over the PAST FOUR WEEKS.

1 Please write in your date of birth:

DAY MONTH YEAR

2 Are you (tick one):

Female Male

3 How often do you leak urine? (Tick one box)

- never 0
 about once a week or less often 1
 two or three times a week 2
 about once a day 3
 several times a day 4
 all the time 5

4 We would like to know how much urine you think leaks.

How much urine do you usually leak (whether you wear protection or not)?
 (Tick one box)

- none 0
 a small amount 2
 a moderate amount 4
 a large amount 6

5 Overall, how much does leaking urine interfere with your everyday life?

Please ring a number between 0 (not at all) and 10 (a great deal)

0 1 2 3 4 5 6 7 8 9 10
 not at all a great deal

ICIQ score: sum scores 3+4+5

6 When does urine leak? (Please tick all that apply to you)

- never – urine does not leak
 leaks before you can get to the toilet
 leaks when you cough or sneeze
 leaks when you are asleep
 leaks when you are physically active/exercising
 leaks when you have finished urinating and are dressed
 leaks for no obvious reason
 leaks all the time

Thank you very much for answering these questions.

Copyright © "ICIQ Group"

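### The SAP pairs p<0.05 with a 90% confidence interval and does not say whether testing is one- or two-sided; separately, it summarises non-normal variables as counts and percentages

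*Combined protocol and SAP*

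**What the plan says.** The Statistical Analysis Plan sets its decision threshold and its interval level in one clause: "the significance will be evaluated at the $p < 0.05$ level with the SPSS 22.0 statistical program at the 90% confidence interval". It does not say whether tests are one- or two-sided, which estimates will carry an interval, or whether the p-value or the interval decides. The tests it names are ANOVA for normal data, Kruskal-Wallis with post-hoc tests for non-normal data, and chi-square for binary data.

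Under Hypothesis of the Study, the null is worded in one direction ("exercise training is no superiority of exercise training with group video conferencing method in urinary incontinence"), and H1 to H6 each say that one-on-one delivery does better.

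On summaries, the SAP gives two rules: "Normally distributed variables will be expressed as mean and standard deviation", and "non-normally distributed variables will be expressed as numbers and percentages". For binary variables it gives a test ("Chi-square test will be used in the evaluation of binary data") but no summary rule. Table 1 lists the primary measures of muscle strength as "PERFECT Scheme -Surface Electromyography".

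**The concern.** There are two separate faults.

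**Interval level.** A test at a given significance level and a confidence interval agree only when their levels correspond. Here they correspond only if testing is one-sided, and the SAP does not say so. If both a p-value and a 90% interval are reported for the same contrast, they can point in different directions, and nothing in the SAP says which prevails. The choice could then be made after the results are known.

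**Summary of non-normal variables.** Counts and percentages describe categories. Surface EMG values, pad-test results, visual analogue scores and questionnaire totals are quantities. If one of them fails the normality check, following the SAP literally gives a frequency list per arm and visit, without a typical value or a spread. For surface EMG this would leave a primary outcome poorly described.

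**Working it through.** **Inputs.** From the SAP: threshold 0.05; interval level 90%; the named tests; no sidedness. From Randomization of the Study Groups: two arms. From Hypothesis of the Study: directional hypotheses. From Annex 4: the ICIQ item scores. Arm sizes used below are assumptions.

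**1. Which test matches which interval.** An interval at level C corresponds to a two-sided test at 1 − C, or a one-sided test at (1 − C)/2.

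| Interval | Critical value | Two-sided level | One-sided level |
|---|---|---|---|
| 90% | 1.645 | 0.10 | 0.05 |
| 95% | 1.960 | 0.05 | 0.025 |

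The SAP's own pair (0.05 with 90%) is reproduced only in the one-sided column.

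**2. What the named tests imply.** For a comparison of two groups, ANOVA has F = t². With an assumed 16 per arm (30 degrees of freedom), the critical F at 0.05 is 4.171 = 2.042², the 95% t value squared. The critical F at 0.10 is 2.881 = 1.697², the 90% t value squared. So a two-group ANOVA at 0.05 matches a 95% interval. This holds for a single contrast. An omnibus test over several visits has no single matching interval, and Kruskal-Wallis and chi-square do not by themselves supply one for a difference in means or risks.

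**3. Worked conflict.** Take a single normal contrast with two-sided p = 0.07, so the estimate is 1.812 standard errors (SE).
- 90% interval: 1.812 ± 1.645 = 0.17 to 3.46 SE, which excludes zero.
- 95% interval: 1.812 ± 1.960 = −0.15 to 3.77 SE, which includes zero.

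**4. How often this could happen.** For a single normal contrast with true effect d in SE units, the chance of conflict is P(90% interval excludes zero) − P(p<0.05).
- No effect (d = 0): 0.100 − 0.050 = 0.050.
- 50% power (d = 1.960): 0.6238 − 0.5000 = 0.1238.
- 80% power (d = 2.802): 0.8763 − 0.8000 = 0.0763.
- Maximum: 0.1254, at d = 1.80.

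These figures are illustrative; they use no effect size, variance or sample size from this trial.

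**5. Error rate if the 90% interval decides.** Two-sided type I error is 0.10 instead of 0.05. In the favoured direction it is 0.05 instead of 0.025.

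**6. Width.** 1.645/1.960 = 0.839, so a 90% interval is about 16% narrower than a 95% one. Conversely, 1.960/1.645 − 1 = 0.192. With t quantiles the widening is 20.4%, 19.8% and 19.6% for an assumed 15, 30 and 40 per arm.

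**7. Summary rule.** The ICIQ total ("ICIQ score: sum scores 3+4+5") adds scores of 0 to 5, one of {0, 2, 4, 6}, and 0 to 10. It can take every whole number from 0 to 5 + 6 + 10 = 21, which is 22 values. If this total is non-normal, the SAP's rule read literally gives up to 22 counts and percentages per arm and visit.

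**The case against.** The strongest defence of the interval level is that the hypotheses are directional, and one-sided 0.05 fits a 90% interval exactly. The SAP also leaves room for unspecified appropriate tests, post-hoc tests and correlations, some of which can be run one-sided. This stands in part: a one-sided intent is not excluded. But it is never declared, and the three main tests named are non-directional.

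A second defence is that the fault concerns reporting only, because p<0.05 is the stated rule. That holds if the p-value from the named tests alone decides. It cannot be taken as given, because the 90% figure stands in the clause that defines how significance is judged.

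A reader might go the other way and infer that the trial will run at a 10% error rate. The documents do not support that either: they state p<0.05 and nowhere say that the interval decides.

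On summaries, counts and percentages are acceptable for an ordinal grade, and some components of the PERFECT scheme may be graded that way. That stands, so the criticism is confined to quantitative outcomes. A reader might also take the mean row in Annex 3 as evidence that group means were intended. It follows three numbered readings and appears to average one patient's repeats, so it shows nothing about group summaries. Nor is there support for inferring that non-normal outcomes would be tested as counts: the SAP sends them to Kruskal-Wallis.

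**Conclusion.** Both faults are real as written, and both are minor.

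The p<0.05 rule and the 90% interval agree only under one-sided testing, which the SAP does not declare and its main named tests do not provide. The consequence is conditional. If the p-value decides, only the reported intervals are at the wrong level. If the 90% interval is used to judge significance, the two-sided type I error doubles from 5% to 10%. The conflict zone is two-sided p between 0.05 and 0.10, shown for a single contrast. The 5.0% to 12.5% chance of landing there assumes one normally distributed contrast and is not an estimate for this trial.

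The summary rule leaves non-normal quantitative outcomes (surface EMG, pad test, visual analogue scores, questionnaire totals) without a typical value or spread. It affects descriptive tables only. The categorical rule may have been attached to non-normal variables by mistake, since binary variables have no summary rule of their own; that is an inference from the text.

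**What to change.** Replace the significance clause with: *two-sided p<0.05, with 95% confidence intervals for the between-group differences; the p-value decides significance*. If one-sided testing is intended, declare it and name tests that deliver it; the 90% interval then fits. Where a rank test is used, name the estimate that will carry the interval.

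Replace the summary rule with: *non-normally distributed quantitative variables as median and interquartile range; categorical variables, and ordinal grades where suitable, as numbers and percentages*.

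Cost: two wording changes, no new data and no extra patients. Under the two-sided option the named tests stay as they are, and reported intervals become about 19-20% wider than at 90%. The one-sided option would also require different tests to be named. Either choice should be fixed before results are seen.

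### The SAP lets an under-specified normality check on the trial's own data choose between ANOVA and Kruskal-Wallis, and neither branch, as written, adjusts for baseline

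*Combined protocol and SAP*

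**What the plan says.** The Statistical Analysis Plan sets a general rule: "appropriate statistical tests will be applied depending on the provision of parametric or non-parametric test conditions". The check is conditional ("If the number of cases is sufficient") and works as follows: "its conformity to the normal distribution will be questioned with the Kolmogorov Smirnov test and normal distribution graphs".

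Two branches follow. If the groups look normal, "the evaluation results at the beginning, 4th week and 8th week will be compared with ANOVA". Otherwise, "if the normal distribution is not met, comparisons will be made with Kruskal Wallis and appropriate post-hoc tests".

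The available text does not give:
- the number of cases that counts as enough;
- the significance level of the normality test, or whether it uses Lilliefors critical values;
- whether it is run by arm, by visit or pooled;
- what happens when test and graph disagree.

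In both branches baseline appears only as one of three visits. No covariate, change score, arm-by-time term or repeated-measures method is named. No outcome has a fixed test. That includes the primary outcome, muscle strength, which Table 1 measures by the PERFECT scheme and surface EMG.

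**The concern.** The hypotheses compare the two arms; the first is "Exercise training with one on one video conference method is more effective in increasing muscle strength in patients with urinary incontinence". A reader should be able to tell from the SAP which quantity decides each hypothesis. Here that is settled only once outcome data have been examined: one branch compares means, the other ranks. PERFECT and EMG serve the same hypothesis and could end up on different scales.

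Much of the answer is also known in advance. Satisfaction and adherence are scored 0-10 (Annexes 7 and 8). The strength grade is coarse and cut off at entry, because the exclusion criteria remove patients whose "Pelvic floor muscle strength is between 0-1 according to the Modified Oxford Scale". A test is not needed to learn that these are not normal.

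Separately, baseline is measured and then not used to sharpen the comparison. In a small trial that can matter more than the choice between means and ranks.

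**Working it through.** **Inputs.** From the documents: two arms; visits at baseline, week 4 and week 8; significance as in "the significance will be evaluated at the $p < 0.05$ level with the SPSS 22.0 statistical program at the 90% confidence interval", taken here as two-sided 0.05 because sidedness is not stated. The available text gives no sample size, standard deviation, effect or baseline correlation, so there is no planned figure to reproduce. Assumed: 1:1 allocation, 24 per arm (16 to 40 where shown), and the distributions below. The comparison is taken as between arms, which is what the hypotheses ask.

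**1. How often the check changes the branch.** Take one rule throughout: any of 2 arms × 3 visits = 6 cells failing at 5% sends the outcome to ranks. For normal data and independent cells, 1 − 0.95^6 = 0.265. Simulation with within-person correlation 0.6 gives about 26%. The skewed example is lognormal with log-SD 0.8 (skewness 3.7).

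| Data, 24 per cell | Lilliefors values | Uncorrected values |
|---|---|---|
| Normal | about 26% flagged | about 0.1% |
| Lognormal | over 99% | about 57% |

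Under a two-cell rule (each arm once), 1 − 0.95² = 0.0975, and simulation gives 9-10% for normal data with Lilliefors values. For 16 / 24 / 32 / 40 per arm:
- skewness 1 goes to ranks in 28 / 38 / 47 / 54% of trials with Lilliefors values, against 0.3-2.4% uncorrected;
- skewness 1.75 goes to ranks in 48 / 64 / 77 / 85%, against 1.7-13% uncorrected.

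The branch therefore depends on sampling variation, sample size and a version of the test that the SAP does not name.

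**2. What this does to error rates.** Under the two-cell rule with Lilliefors values, the type I error of the whole two-stage procedure is 0.044-0.058 across all settings. ANOVA and Kruskal-Wallis disagree on significance in 1-3% of trials with no effect and in 2-14% with a true effect of 0.7 SD. The choice can change a verdict, but it does not materially inflate false positives.

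**3. What the missing covariate costs.** Pad-test-like scenario: lognormal, log-SD 0.8, correlation 0.6 with baseline, 40% less leakage in one arm, 24 per arm.
- Log-scale effect: |ln 0.6| / 0.8 = 0.511 / 0.8 = 0.64 SD.
- Unadjusted: 0.6385 × √(24/2) = 2.21; power ≈ Φ(2.21 − 1.96) = 60% by normal approximation.
- With baseline: residual SD shrinks by √(1 − 0.6²) = 0.8, so 2.21 / 0.8 = 2.76; power ≈ Φ(2.76 − 1.96) = 79%.

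Simulation, which allows for the small sample, gives:

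| Analysis | Power |
|---|---|
| Raw means | 47-48% |
| Kruskal-Wallis | about 55% |
| Two-stage rule, six cells | about 55% |
| Unadjusted log-scale test | 58% |
| Rank ANCOVA | 73% |
| Log-scale model with baseline | 76-77% |

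The step from about 55% to 58% comes from the scale. The step from 58% to 76-77% comes from the covariate.

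**4. Range over the correlation.** Normal data, effect 0.7 SD, 24 per arm, correlation 0.3 / 0.5 / 0.7: ANCOVA has simulated power 0.69 / 0.78 / 0.91, ANOVA on week-8 values 0.67 / 0.67 / 0.65, and Kruskal-Wallis 0.64 / 0.64 / 0.62. By formula, 80% power needs 30 / 25 / 17 per arm with ANCOVA, against 33 unadjusted.

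**The case against.** The best defence is that the rule works tolerably. In the pad-test scenario it holds type I error near 5%, matches Kruskal-Wallis for power and beats raw means. Graphs are read alongside the test, so a mechanical six-cell rule is only one reading. All of this stands, and it limits the point.

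Three stronger readings are tempting, and the documents do not support them.

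- *Only the rank branch loses baseline, and it must.* The ANOVA branch names no baseline covariate either. Kruskal-Wallis takes no covariate, but it can be run on change scores (power 0.49 / 0.63 / 0.84 in the step 4 setting), and rank ANCOVA reaches 0.66 / 0.74 / 0.87. The SAP specifies neither. The gap lies in both branches and is not caused by the normality check.
- *Normal data are often misrouted and skewed data often pass.* These two harms belong to different versions of the test. Under the six-cell rule, Lilliefors values misroute normal data but catch almost all the skewed data. Uncorrected values do the reverse.
- *The choice is made on unmasked data.* The available text does not describe the analyst's masking. It supports only that the choice is made on outcome data.

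Nor does it help to complain that raw values are tested instead of residuals. Within a group, subtracting the mean leaves the Kolmogorov-Smirnov statistic unchanged when mean and SD are estimated.

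**Conclusion.** The point holds in two parts. First, the analysis of every outcome is left to a check whose trigger, version and unit are open, so the quantity being compared is not fixed in advance. That is a defect of specification. A reader might infer a serious loss of error control or power from it, but the simulations show about 4-6% type I error and almost no power cost relative to Kruskal-Wallis. Second, neither branch uses the baseline value, and this is the larger practical loss: roughly 20 percentage points of power in the pad-test scenario, and little at a correlation of 0.3.

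The text alone establishes the open choice and the absent covariate. The sizes rest on assumed sample size, distributions, effect and correlations. The change is worth making because it is nearly free, not because the present rule would invalidate the trial.

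**What to change.** Delete the normality check as selector and name one between-arm week-8 analysis per outcome, before outcome data are examined:

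- **Surface EMG (resting tone, MVC, endurance), PERFECT endurance, repetitions and fast contractions, and questionnaire totals:** linear model with arm and the outcome's own baseline value, with robust standard errors as the only stated inference.
- **1-hour pad test:** the same model on log(grams + 1), reported as a ratio.
- **PERFECT power, and any other ordinal component such as ECT:** proportional-odds model with arm and baseline. Annex 3 records three trials and their mean, so power may fall in thirds; the model accepts that.
- **Satisfaction and adherence VAS items:** proportional-odds model without a baseline term, since they ask about treatment already received.

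Analyse week 4 with the same models as a secondary time point. Name rank ANCOVA as a sensitivity analysis that cannot replace the main result.

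The cost is SAP wording, with no added patients, visits or measurements. The one small downside is that the pad test is then read as a ratio and the grade as an odds ratio.
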